4.4 MISSING DATA

Missing values represent a potential source of bias in a clinical trial. Hence, every effort will be undertaken to fulfill all the requirements of the protocol concerning the collection and management of data; however, some missing data is inevitable. As the primary objective of this study is safety and tolerability, no imputation or adjustment for missing data will be done.

4.5 SUBGROUP ANALYSES

Due to the small treatment group sizes, subgroup summaries are not planned.

5 TECHNICAL PERFORMANCE OF THE DEVICE

The technical performance of the device will be summarized for each active treatment. The incidence of the following will be summarized: ventilator/CPAP tubing detachments, aerosol tube detachments, aerosol tube condensate obstruction, proximal pressure port obstructions, study drug leakage (either liquid or aerosol), occurrence of alarms signals (before, during, and after dosing), automatic system shutdowns, loss of inspiratory flow, inability to maintain nCPAP, occurrence of error codes.

In addition, the weight and/or volume of liquid in all traps will be summarized as continuous variables.

6 SAFETY ANALYSES

6.1 SAFETY POPULATION

The safety population includes all subjects who received any study medication. All safety assessments will be based on this population.

6.2 SAFETY ENDPOINTS

Safety endpoints include:

- Early termination of therapy
- Peri-dosing events
- AEs and ADEs
- Air Leak (especially pneumothorax)
- Death
- Physical examinations
- Assessments of the following:
 - PCO₂
 - Serum electrolyte measurements (Na⁺, Cl⁻, K⁺)
 - Body weight
 - Vital signs
 - Gastric liquid volume
 - Defecation
 - O₂ saturation, as determined by SpO₂
 - Chest radiograph, as applicable
- Respiratory Support:
 - nCPAP settings (cm H₂O) (or other means of ventilator support)
 - Need for endotracheal intubation and IMV parameters
 - Oxygen support (FiO₂)
- Complications of prematurity (ie, intraventricular hemorrhage [IVH], cystic periventricular leukomalacia [PVL], pulmonary hemorrhage, necrotizing enterocolitis [NEC], patent ductus arteriosus [PDA], sepsis, retinopathy of prematurity [ROP])

6.3 EXTENT OF EXPOSURE

All subjects randomized to active treatment are to receive one dose of study medication. Subjects will receive 30, 45, 60, or 90 minutes of aerosolized lucinactant. The number of subjects who

receive a repeat dose and the number of subjects whose study treatment is terminated early will be summarized.

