Control Arm (n = 8): Continuous nCPAP

Each dosing group will complete study dosing and all active subjects will complete 72 hour safety assessments and procedures before the SRC review. The SRC will review all available safety data (to include study-related adverse events [AEs], including adverse device effects [ADEs], serious adverse events [SAEs], and additional safety endpoints). Enrollment will continue in the next dosing group without pause from the previous dosing group; however, if the SRC identifies safety concerns that would preclude dosing, enrollment will stop until these safety concerns are addressed and the SRC recommends resuming enrollment.

Repeat dosing will be allowed in each dosing group. Subjects meeting the repeat dosing criterion will receive an additional treatment of the same dose. Repeat dosing will be allowed between 2 hours and 24 hours after completion of the initial dose if subjects require a sustained need for supplemental oxygen at or above the qualifying FiO₂ level for study entry (ie, 0.25) for at least 30 minutes to maintain SpO₂ of 88% to 95%.

Subjects will be followed for safety evaluations (including, but not limited to, AEs and concomitant medications) until the subject is

36 weeks PMA or is discharged. A final visit will occur at 36 weeks PMA or at the time of discharge or withdrawal (whichever occurs first) for all subjects.

Inclusion Criteria:

1. Signed ICF from legally authorized representative;
2. Gestational age 26 to 28 completed weeks PMA;
3. Successful implementation of controlled nCPAP within 90 minutes after birth;
4. Spontaneous breathing;
5. Chest radiograph consistent with RDS;
6. Within the first 20 hours after birth, requires an nCPAP of 5 to 6 cm H₂O to maintain SpO₂ of 88% to 95% with an FiO₂ of 0.25 to 0.50 that is clinically indicated for at least 30 minutes. Transient (<10 minutes) FiO₂ excursions below 0.25 or above 0.50 do not reset the 30 minute requirement.

Exclusion Criteria:

1. Heart rate that cannot be stabilized above 100 beats per minutes within 5 minutes of birth;
2. Recurrent episodes of apnea occurring after the initial newborn resuscitation period (ie, 10 minutes after birth) requiring intermittent positive pressure breaths using inflating pressures above the set CPAP pressure administered manually or mechanically through any patient interface;
3. A 5 minute Apgar score < 5;

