5.2.5 Repeat Dosing

In order to ensure the safety of repeat dosing, specifically in regards to AEs and electrolyte changes (such as sodium and potassium levels), and to ensure subjects with a demonstrated need receive treatment, 1 repeat dose will be allowed for all dosing groups. The repeat dose will consist of repeating the same dose and will occur between 2 and 24 hours after the initial dose, if the repeat dosing criterion is met. The repeat dosing criterion is defined as at least 2 hours, but no more than 24 hours, after dosing and the subject must require a sustained need for supplemental oxygen at or above the qualifying FiO_2 level for study entry (ie, 0.25) for at least 30 minutes to maintain SpO_2 of 88% to 95%.

As with the initial dose, the IWRS will be used to receive the study drug assignments, and all other procedures that were performed for the initial dose will be followed for the administration of the repeat dose.

[figure not shown]
If, in the opinion of the PI, repeat dosing would compromise the safety of the subject, repeat dosing will not occur.

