5.7 Study Compliance

Study compliance will be based on the actual delivery time of lucinactant for inhalation in comparison to the subject's randomized aerosolization time. Aerosolization time will be tracked by the ACU, which will display a continual count of lucinactant exposure time throughout the aerosol delivery period. The length of lucinactant exposure time (as observed through aerosol delivery and ACU display) will be documented in the study eCRF. The ACU will also display an interface to allow for emergent aerosol discontinuation. PIs are to discontinue aerosol delivery if a potential safety risk to the subject is identified at any point during the aerosol delivery period.

The number of subjects randomized but not treated, and the number of subjects prematurely discontinued from aerosol delivery will be recorded in the eCRF and summarized in the study report.

No diaries will be required since lucinactant for inhalation will be administered at the clinical site.

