7.1.5 Monitoring of Carbon Dioxide Levels

PCO₂ measurements for subjects in both the active and control groups will be resulted through the use of continuous transcutaneous monitor.

PCO₂ monitoring must be initiated following randomization (for subjects randomized to the active study arm, monitoring must be initiated at least 30 minutes before the start of ADS

delivery) and continue for 72 hours post randomization. The transcutaneous monitor must be calibrated for accuracy against blood gas values (arterial, capillary or venous) at the time of initial set-up, and recalibrated as necessary in accordance with local institutional practices to ensure accuracy of the monitor output.

In the eCRF, PCO₂ values will be recorded every 15 minutes through 3 hours after randomization, and every 6 hours from randomization through 72 hours.

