7.1.7 Serum Electrolytes

Serum electrolytes (Na⁺, Cl⁻, K⁺, and Total CO₂) will be measured 24 hours from the time of randomization (± 6 hours).

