3.3 STUDY AND CONCOMITANT MEDICATION

3.3.1 Compliance

Compliance summary for this study is not applicable as all subjects will be administered at least one dose by study staff in the NICU.

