6.5.3 Electrolytes

Sodium, chloride, potassium, and total carbon dioxide (CO₂) will be summarized at 24 hours post randomization as continuous variables. Clinically significant values will also be recorded as AEs.

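### The SAP drops the compliance summary that Protocol 5.7 defines, plans no table of aerosol minutes, and never shows separately what follows the second dose

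*SAP*

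**What the plan says.** SAP 3.3.1 states: "Compliance summary for this study is not applicable as all subjects will be administered at least one dose by study staff in the NICU". Protocol 5.7 says otherwise: "Study compliance will be based on the actual delivery time of lucinactant for inhalation", set against the aerosol time to which the subject was randomized. The same section has exposure time entered in the eCRF and foresees subjects who are randomized but not treated, or stopped early. For the study report it names two counts, those untreated and those stopped prematurely.

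SAP 6.3 gives the planned durations (30, 45, 60 or 90 minutes) and says that the number of subjects who "receive a repeat dose and the number of subjects whose study treatment is terminated early will be summarized". SAP 3.3.2 and Table 3.2 add the number of treatments received. Table 5.2 and a listing cover early termination.

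Protocol 5.2.5 introduces repeat dosing with this purpose: "In order to ensure the safety of repeat dosing, specifically in regards to AEs and electrolyte changes". SAP 2.2.2 repeats it. SAP 6.4 summarises AEs by treatment group, which SAP 2.2.1 defines as each active dose plus combined controls. Electrolytes "will be summarized at 24 hours post randomization as continuous variables" (SAP 6.5.3).

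The peri-dosing window is 2 hours from the start of administration in Protocol 3.3 and 8.2, the SAP Executive Summary and the SAP 2.2.4 schedule. SAP 1.2.3 gives 24 hours.

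**The concern.** Concentration and delivery rate are fixed in this trial, so the dose level is set by duration and minutes are the measure of dose. A plan that declares compliance inapplicable leaves the reader unable to see how much of the assigned dose an early-stopped infant received.

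The second gap concerns a stated purpose. If repeats are allowed partly to learn whether a second dose is safe, the report should show what happened after it. Under the plan as written, a reader can see how many infants had a repeat but not which events followed it. The secondary objective is a maximum tolerated dose judged within each dosing group, and Protocol 6.1 describes the next dose level as including a potential repeat. The tolerability of that regimen therefore rests partly on evidence that the planned tables do not isolate.

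**Working it through.** **Minutes to dose.** Inputs from Protocol 2.2.3.3: output 1.2 ml/min, 30 mg TPL/ml, delivered fraction 0.35, carrier flow 3 L/min, minute ventilation 0.4 L/min/kg.

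- Aerosol concentration: 1.2 × 30 × 0.35 / 3 = 4.2 mg TPL/L.
- Theoretical inhaled rate: 4.2 × 0.4 = 1.68 mg/kg per minute.
- Durations for 50, 75, 100 and 150 mg/kg: dose / 1.68 = 29.76, 44.64, 59.52 and 89.29 minutes. These round to the protocol's 30, 45, 60 and 90.

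The stop at 20 minutes below is an illustration; 20 × 1.68 = 33.6 mg/kg in any group.

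| Group | Assigned minutes T | One full dose, 1.68T (mg/kg) | Two full doses (mg/kg) | Stop at 20 min, 20/T |
|---|---|---|---|---|
| I | 30 | 50.4 | 100.8 | 67% |
| II | 45 | 75.6 | 151.2 | 44% |
| III | 60 | 100.8 | 201.6 | 33% |
| IV | 90 | 151.2 | 302.4 | 22% |

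In Group IV, stops at 5 and 85 minutes give 5 × 1.68 = 8.4 and 85 × 1.68 = 142.8 mg/kg. Each is one early termination in the planned count.

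**Peri-dosing window.** The Protocol Summary states: "Repeat dosing will be allowed between 2 hours and 24 hours after completion of the initial dose". After a full first dose, the earliest repeat is therefore T + 2 h after dose 1 began.

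- A 2-hour window counted only from dose 1 has closed T minutes earlier: 30, 45, 60 or 90 minutes before any repeat may start.
- A 24-hour window counted from dose 1 covers (22 − T/60)/22 of the 22-hour repeat window: 21.5/22 = 98% for T = 30, falling to 20.5/22 = 93% for T = 90. It would mix events of the two doses.
- A 2-hour window that restarts at each dose captures both, but Table 6.1 has no planned split by dose.

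**Electrolytes.** Protocol 7.1.7 sets one draw: electrolytes "will be measured 24 hours from the time of randomization", ± 6 h, so 18 to 30 h. For PCO2 in the active arm, "monitoring must be initiated at least 30 minutes before the start of ADS" delivery, and it begins after randomization. Dose 1 therefore starts 0.5 to 2 h after randomization, lasts 0.5 to 1.5 h and ends at 1.0 to 3.5 h. A repeat may then start at 3.0 to 27.5 h. The share of the repeat window lying after the draw is (end of dose 1 + 24 − draw time)/22:

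- draw at 18 h: 7.0/22 = 32% to 9.5/22 = 43%
- draw at 24 h: 1.0/22 = 5% to 3.5/22 = 16%
- draw at 30 h: 0%

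These are shares of the window, not of infants. A value from a two-dose infant may precede or follow dose 2, and SAP 6.5.3 does not distinguish the two.

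**Planned outputs.** Tables 6.1, 6.2, 6.3.1 and 6.4.1 are not planned by dose number. The listings include none for all AEs, and the SAE listing described in SAP 6.4.4 does not mention onset relative to dose.

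**The case against.** Much of the plan is sound, and several stronger readings fail.

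- **A required report item is missing.** A reader might infer this from the conflict. But Protocol 5.7 sends only two counts to the study report, and SAP 3.2 and 6.3 supply them. The conflict is with the protocol's definition of compliance and with the reason given in SAP 3.3.1.
- **Exposure is unknown.** It is not. SAP 6.3 and Table 3.2 show how many infants had one or two treatments, and an infant not stopped early received the assigned minutes. The early-termination listing might show minutes for the others, but its columns are unspecified and a listing is not a summary.
- **Events after dose 2 are lost or wrongly assigned.** They are collected and counted, and charging them to the assigned group is right, because the regimen is a dose plus one permitted repeat. They are only not isolated.
- **The peri-dosing window excludes dose 2.** Protocol 5.2.5 applies the initial-dose procedures to the repeat, so a per-administration reading is natural. The text does not say so, and the 24-hour version in SAP 1.2.3 conflicts with it.
- **The electrolyte table hides a dose-2 effect.** The limit comes mainly from the protocol's single draw, and no on-study baseline electrolyte is scheduled. At the nominal 24 h, 84 to 95% of the repeat window comes before the draw. Splitting the values cannot measure an effect of dose 2.
- **SAP 4.5 forbids the display.** It sits in the efficacy section and does not govern safety displays.

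It is also fair that cells will be small. If 4 of 8 infants in a group repeat (an assumption), no event after dose 2 leaves a one-sided 95% upper limit of 1 − 0.05^(1/4) = 53%. With 16 pooled over four groups it is 1 − 0.05^(1/16) = 17%. These limits come from sample size and remain after any change to the tables. They favour an all-active display over splits by group.

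**Conclusion.** The point holds in limited form. The reason in SAP 3.3.1 is wrong on the protocol's own terms: the 32 planned controls receive no dose, some active infants may go untreated, and receiving one dose is not receiving the assigned minutes. No planned table reports minutes, and the practical loss is confined mainly to early stops, where one count can stand for anything from a small fraction to nearly all of the assigned dose. Repeat-dose safety is a stated purpose for which no output isolates the evidence. The peri-dosing definition is inconsistent and needs a single rule.

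The mg/kg figures rest on the protocol's theoretical inhalation formula, and the timing figures on full first doses given within protocol windows. How many infants will repeat is unknown: the documents give no expected rate, and their FiO2 thresholds differ (0.25 in Protocol 5.2.5, 0.35 in SAP 2.2.2). The size of the second gap therefore cannot be stated in infants. This should be corrected, but it does not threaten the trial's design or its main safety tables.

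**What to change.** 1. **SAP 3.3.1 and 6.3.** Replace the statement that compliance does not apply with a summary of actual minutes and percent of assigned time for dose 1 and for dose 2, and cumulative minutes, by active group and for all active infants.
2. **Peri-dosing events.** Correct SAP 1.2.3 to 2 hours, state that the window applies to each administration, and show dose 1 and dose 2 separately in Table 6.1.
3. **Events after dose 2.** Add one descriptive display or listing, mainly for all active infants given two doses, of AEs, air leaks and SAEs that began after dose 2 started, with the number given dose 2 as denominator. In a listing, flag each electrolyte value as drawn before or after dose 2, without claiming that this measures an effect of the second dose.
4. **SRC.** Supply these displays at each review.

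Keep the assigned-dose columns primary. SAP 4.5 needs no exception.

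The cost is some extra programming. Aerosol minutes, delivery start and completion times and AE onset times are already recorded (Protocol 5.7, 8.2 and 9). The electrolyte flag needs the draw time, which SAP 9.2 should provide if the draw is treated as a timed event. No visit, sample or infant is added. Two-dose infants are selected by continuing oxygen need, and follow-up after dose 2 is far longer than before it. The display is therefore descriptive only, and just the two 2-hour windows cover equal lengths of time.

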6.4 ADVERSE EVENTS

All AEs will be coded by preferred term and system organ class (SOC) from the Medical Dictionary for Regulatory Activities (MedDRA), version 16.1 or above, and will be reviewed by the medical monitor or designee. All AEs will be summarized as categorical variables (frequency and percent) by treatment group unless otherwise indicated. AEs that are related to the device (ADEs) will be summarized with all AEs and separately. AEs will not be compared between treatment groups.

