- In the PI's best medical judgment, initiating or continuing the subject's exposure to lucinactant for inhalation is not in the best interest of the subject's safety, such as hemodynamic instability.
- Signs of acute respiratory deterioration as evidenced by an increased respiratory rate or an observed increase in respiratory effort (work of breathing) plus at least one of the following:
 - a) An FiO₂ ≥ 0.70 or a sustained (≥ 10 minutes) increase from baseline by ≥ 0.30 to maintain adequate oxyhemoglobin saturation (SpO₂ $\geq 88\%$),
 - b) A PCO₂ > 70 mm Hg or a progressive increase from baseline to ≥ 20 mm Hg above baseline and confirmed with a blood gas,
 - c) Recurring episodes of bradycardia defined as a heart rate < 100 bpm for ≥ 20 seconds,
 - d) A sustained apneic event, defined as apnea for at least 20

seconds in duration and meeting at least one of the following: (1) HR < 100 bpm, (2) desaturation (oxygen saturation < 80%), (3) requirement for IPP breaths using inflating pressures above the set CPAP pressure administered manually or mechanically through any patient interface.

Enrollment hold criteria:

The study will be placed on enrollment hold until further evaluation by the SRC if one of the following criteria are met:

- If > 2 subjects per dosing group experience a SAE related to lucinactant for inhalation administration
- If ≥ 1 subject dies during first 12 hours following and related to lucinactant for inhalation administration

Statistical Analysis: The statistical analysis of both the primary and secondary safety and tolerability objectives will be based on all randomized preterm neonates in the study. In addition, data from all evaluable preterm neonates will be analyzed for efficacy signals as an exploratory endpoint. No hypothesis testing or statistical comparisons will be performed.

Interim Analyses: All available safety endpoint data captured from randomization to completion of 72 hours for active subjects, and all available safety endpoint data for control subjects, will be evaluated by the SRC. As this is an open-label study with no hypothesis testing, no adjustments for *p*-values are required or employed for the interim analyses.

TABLE OF CONTENTS

TITLE PAGE	1
AEROSURF PROTOCOL SUMMARY	3
TABLE OF CONTENTS	15
LIST OF ABBREVIATIONS	20
1 INTRODUCTION.....	22
1.1 Treatment of Neonatal Respiratory Distress Syndrome	22
1.1.1 Continuous Positive Airway Pressure in Neonatal Respiratory Distress Syndrome	23

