3.1 Primary Objective

The primary objective of this study is to evaluate the safety and tolerability of lucinactant for inhalation, administered as an aerosolized dose in 4 escalating doses to a preterm, neonatal population 26 to 28 completed weeks PMA receiving nCPAP for RDS compared with neonates receiving nCPAP alone.

Safety and tolerability will be evaluated using the same measures and assessments that have been used in Protocol 03-CL-1201, which has shown lucinactant for inhalation up to 75 mg/kg to be generally safe and well-tolerated in infants 29 to 34 completed weeks PMA.

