13.3 Sample Size and Randomization

Sample size is not based on statistical estimation for this phase 2 study. The number of subjects randomized (approximately 8 in each active group and approximately 8 in each control group) will be considered sufficient to establish safety and tolerability before proceeding to the next higher dose. The total of approximately 32 subjects assigned to the active arm and approximately 32 subjects for the control arm for the entire study is considered sufficient to assess overall safety and tolerability.

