Dosing Group I	Active Arm : 50 mg TPL/kg Delivered over 30 minutes in conjunction with nCPAP 1 repeat dose allowed if repeat dosing criterion met	n=8
	Control Arm : Continuous nCPAP	n=8
Dosing Group II	Active Arm : 75 mg TPL/kg Delivered over 45 minutes in conjunction with nCPAP 1 repeat dose allowed if repeat dosing criterion met	n=8
	Control Arm : Continuous nCPAP	n=8
Dosing Group III	Active Arm : 100 mg TPL/kg Delivered over 60 minutes in conjunction with nCPAP 1 repeat dose allowed if repeat dosing criterion met	n=8
	Control Arm : Continuous nCPAP	n=8
Dosing Group IV	Active Arm : 150 mg TPL/kg Delivered over 90 minutes in conjunction with nCPAP 1 repeat dose allowed if repeat dosing criterion met	n=8
	Control Arm : Continuous nCPAP	n=8

Note: TPL = Total Phospholipids

Dosing Group I will complete study dosing and all active subjects will complete 72 hour safety assessments and procedures before the Safety Review Committee (SRC) review. The SRC will complete their review of all available Dosing Group I safety data (to include study-related adverse events [AEs], serious adverse events [SAEs], and additional safety endpoints) before recommending advancing enrollment to additional dosing groups. If the SRC concludes there are no safety concerns that would preclude proceeding to the next higher dose, dosing will commence in Dosing Group II. Likewise, the SRC will review the safety and tolerability of this dose and each succeeding dose, with dosing proceeding in the next dosing group if the SRC determines there are no safety concerns.

Repeat dosing will be allowed in each dosing group. Subjects meeting the repeat dosing criterion will receive an additional treatment of the same dose. Repeat dosing will be allowed between 2 and 24 hours after completion of the initial dose.

Subjects will be followed for safety evaluations (including, but not limited to, AEs and concomitant medications) until the subject is 36 weeks PMA or is discharged. Descriptive statistics (number of subjects, percent, mean, standard deviation, median, minimum, maximum) will be presented by treatment group, defined as each of the active doses (n = 8; 32 subjects total) and the all controls combined (n = 32). A final visit will occur at 36 weeks PMA or at the time of discharge or withdrawal (whichever occurs first) for all subjects.

Key safety and tolerability endpoints in the study include:

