1.2 OBJECTIVES

1.2.1 Primary Objective

The primary objective of this study is to evaluate the safety and tolerability of aerosolized surfactant, specifically lucinactant for inhalation (30 mg TPL/ml), administered in escalating theoretical inhaled doses of 50, 75, 100, and 150 mg TPL/kg to preterm neonates 26 to 28 completed weeks (28 weeks 6 days) PMA who are receiving nCPAP for RDS, compared to neonates receiving nCPAP alone. The primary objective of this study will be assessed based on safety evaluations, including adverse events (AEs) and serious adverse events (SAEs), and tolerability of the device, reported from the time of randomization until 36 weeks PMA.

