2.2.3 Sample Size Justification

The number of subjects randomized (8 in each active group and 8 in each control group) is considered sufficient to establish safety and tolerability before proceeding to the next higher dose. A total of approximately 32 subjects assigned to the active arm and approximately 32 subjects for the control arm for the entire study is considered sufficient to assess the overall safety and tolerability and to select safe and well-tolerated doses. Statistical sample size calculations were not performed.

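### Safety against nCPAP alone is the primary objective, but the plan gives no estimate of the difference and no interval, and it says 8 infants per dose can establish safety

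*SAP*

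**What the plan says.** **The question is comparative.** Protocol section 3.1 asks about safety and tolerability in infants "receiving nCPAP for RDS compared with neonates receiving nCPAP alone". SAP section 1.2.1 repeats this for infants "who are receiving nCPAP for RDS, compared to neonates receiving nCPAP alone". About 32 of the 64 infants are randomized to nCPAP alone.

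**The analysis is counts and percentages.** SAP section 6.4: "All AEs will be summarized as categorical variables (frequency and percent) by treatment group unless otherwise indicated". The same paragraph ends: "AEs will not be compared between treatment groups". The SAP Executive Summary lists the statistics: "Descriptive statistics (number of subjects, percent, mean, standard deviation, median, minimum, maximum) will be presented by treatment group". There, treatment group means each active dose (n = 8) and all controls combined (n = 32). The Statistical Analysis paragraph of the protocol summary adds: "No hypothesis testing or statistical comparisons will be performed". No section of either document specifies a confidence interval for an event rate or a difference, and SAP section 8.3, on statistical methods, is marked not applicable.

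**The assurance is strong.** Protocol section 13.3 says about 8 per active and 8 per control group "will be considered sufficient to establish safety and tolerability before proceeding to the next higher dose". SAP section 2.2.3 says the same number "is considered sufficient to establish safety and tolerability before proceeding to the next higher dose". Each section also discloses that the number does not come from a statistical calculation. For the study as a whole, both use the softer verb *assess*.

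**The concern.** A randomized control arm is there so that the excess risk on active treatment can be estimated. A rule against comparing adverse events works against that purpose, and leaving out hypothesis tests does not require it: a difference with a descriptive interval is estimation.

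Precision matters most where the counts are smallest. The results feed the maximum tolerated dose (Protocol 3.2, SAP 1.2.2) and the choice of safe and well-tolerated doses (SAP 2.2.3). A column showing 0 of 8 says nothing about how large a risk it leaves open, and the word *establish* invites the reader to take it as reassurance. The protocol's account of the study in older infants (section 2.2.3.2) shows the difficulty. It notes higher rates of several adverse events, air leak among them, in the first active group, and then says the small numbers make comparison hard. Comparisons will be made, so the plan should say how and with what precision.

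**Working it through.** **1. The plan's own figure.** No alpha, power, event rate or precision target is given, so there is no statistical derivation to reproduce. The arithmetic is consistent: 4 dosing groups × (8 active + 8 control) = 64, with 32 per arm.

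**2. What zero events can exclude.** For 0 events in *n*, the exact (Clopper-Pearson) 95% upper limit is 1 − 0.025^(1/*n*) two-sided and 1 − 0.05^(1/*n*) one-sided.

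| Result | Two-sided 95% | One-sided 95% |
|---|---|---|
| 0/8 (one dose) | 1 − 0.6306 = 36.9% | 1 − 0.6877 = 31.2% |
| 0/32 (all active) | 1 − 0.8911 = 10.9% | 1 − 0.9106 = 8.9% |

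**3. How often 8 infants would look clean, and how often the hold rule would be met.** Protocol section 6.2 suspends enrollment when more than 2 infants in a dosing group have a dosing-related SAE, which means 3 or more of 8 treated. P(no event) = (1 − *p*)^8, and P(3 or more) = 1 − P(0) − P(1) − P(2). The true risks *p* are assumed, because the documents give none.

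| Assumed true risk | P(0 of 8) | P(3 or more of 8) |
|---|---|---|
| 10% | 43% | 3.8% |
| 20% | 17% | 20% |
| 30% | 5.8% | 45% |

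For example, at 20%: 1 − 0.1678 − 0.3355 − 0.2936 = 0.203.

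**4. Width of the missing intervals.** All counts here are illustrative assumptions; none is in the documents.

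- Single rate, 2/8: exact 95% interval 3.2% to 65.1%.
- All-active 6/32 against control 3/32, Newcombe method. The Wilson limits are 0.0889 to 0.3531 and 0.0324 to 0.2422, and the difference is 0.1875 − 0.09375 = 0.094.
  - Lower limit: 0.09375 − √[(0.1875 − 0.0889)² + (0.2422 − 0.09375)²] = −0.084.
  - Upper limit: 0.09375 + √[(0.3531 − 0.1875)² + (0.09375 − 0.0324)²] = +0.270.
  - In points: +9.4 (−8.4 to +27.0).
- One dose, 1/8, against pooled control, 3/32: +3.1 points (−14.9 to +38.3).
- 0/8 against 0/32: 0 points (−10.7 to +32.4).

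**5. Can the contrast be computed from the planned tables?** Not with certainty. SAP section 6.1 defines the safety population as infants who received study medication. Read literally, that leaves out the nCPAP-only arm, yet the safety tables listed in the SAP use this population. The SAP Executive Summary instead bases the safety analysis on all randomized infants. The two must be reconciled first.

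**6. Which events are ascertained alike?** Under Protocol section 7.1.1, heart and respiratory rate are documented every 5 minutes during dosing for Groups I and II and every 15 minutes for Groups III and IV. Controls have one additional reading, 15 minutes after randomization. Oximetry is continuous in both arms (7.1.3), but section 7.1 requires continual clinical assessment specifically during aerosol delivery. The first worsening criterion in section 7.5.1 is surfactant need after lucinactant exposure, which a control cannot meet as worded. Death, SAEs and air leak can be counted from randomization in both arms, because section 9 starts adverse-event assessment at randomization for everyone.

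**The case against.** The strongest reply is that the sentence in SAP 6.4 only means no formal testing. That is probably the intent, since SAP sections 1.3, 4.3 and 8.4 all exclude testing, and for a phase 2a escalation study that choice is acceptable and disclosed. A reader might infer that the primary objective is never estimated. The documents do not support this. Rates are presented by dose beside pooled controls, the adverse-event and SAE tables include orderings by total active group, and Figures 2.1 to 2.3 plot all active against control for FiO₂, SpO₂ and PCO₂. The primary endpoints also extend beyond adverse events. The gap is narrower: no estimate of the difference and no precision. Those figures show that an all-active contrast is already planned for physiology, though not for safety events.

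A reader might also infer that escalation rests on a bare 0/8, or that the sample is too small. Neither follows. A committee reviews all adverse events, SAE cases, summary tables of the safety endpoints and aggregated controls (Protocol 6.1), with hold rules and experience in older infants behind it. The 37% figure describes what one group of 8 can exclude on its own. It does not describe how the escalation decision is made, and it is no argument for more infants.

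Two parts of the objection stand and limit the remedy. A difference with an interval could itself be read as a statistical comparison, so the protocol summary must be aligned. An interval around an unequally ascertained event would also give false precision to a biased, open-label contrast. That anyone could compute intervals from the counts is true, but it does not repair the word *establish*.

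**Conclusion.** The point holds in limited form. A comparative primary objective is paired with a rule against comparing adverse events, and no interval is planned for any rate or difference. The claim that 8 per group can establish safety exceeds what 8 infants can show: 0/8 leaves risks up to 36.9% open (two-sided exact 95%; 31.2% one-sided), and 0/32 up to 10.9% (8.9% one-sided). These limits assume independent infants with a common risk. Siblings from multiple births are randomized independently, so some clustering is possible and would widen them. The assumed risks and example counts illustrate scale only and predict nothing about the trial. Omitting hypothesis tests is not a fault. The change should be made, but it alters no escalation rule, patient number or data collection.

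**What to change.** 1. **SAP 6.4 and the protocol summary.** Replace the no-comparison sentence, and align the protocol's exclusion of statistical comparisons. State that no hypothesis tests will be done, but that key safety events will be reported with exact 95% intervals by dose, for all active and for control. Add the all-active minus control difference with a Newcombe 95% interval, labelled descriptive.
2. **SAP 6.1.** Reconcile the safety population with the all-randomized statement in the Executive Summary, so that nCPAP-only infants are in the safety tables.
3. **Scope of the differences.** Limit them to events ascertained alike in both arms over a common window from randomization, such as death, SAEs and air leak. Report bradycardia, desaturation, apnea and worsening by group, with a note that ascertainment or wording differs between arms.
4. **Protocol 13.3 and SAP 2.2.3.** Replace *establish* with *provide a preliminary assessment of*, and state the 0/8 and 0/32 limits with their one- or two-sided convention. Keep the disclosure that no sample-size calculation was done, and label any example counts as illustrative.

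Cost: a few table columns, matching edits in two documents and a less favourable stated assurance. No added infants, tests or assessments.
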